2.2 Secondary Aim: To test dose vs. synergy effects of de-coupling therapy by comparing the CBT-DC group to the CBT-Original (O) group on alcohol outcomes. We predict that the CBT-DC group will have superior alcohol outcomes compared to the CBT-O group. This result would show the dose-response effects of de-coupling therapy on alcohol outcomes (6 vs. 3 DC sessions) and confirm that the de-coupling therapy effect on alcohol outcomes is not dependent upon its combination (synergy) with anxiety reduction elements. Alternatively, if CBT-O is superior to CBT-DC, then the critical role of synergy would be demonstrated.

2.3 Tertiary Aim: To test the dose effects of anxiety reduction therapy by comparing the CBT-AR group to the CBT-O group on alcohol outcomes. We predict that the CBT-O group will have superior alcohol outcomes compared to the CBT-AR group. Assuming synergy was ruled out in the Secondary Aim, this result would further confirm the hypothesized dose-response effects of de-coupling therapy on alcohol outcomes (3 vs. zero DC sessions). Alternatively, if the CBT-AR group is superior to the

CBT-O group, then a critical role for the higher dose of anxiety reduction therapy would be demonstrated.

2.4 Mechanism Manipulation Checks: Compare groups on pre- to post-treatment change in mechanism process measures. Determining that the interventions affected the targeted mechanism in the dose-dependent manner intended (e.g., reduction in AR-AOEs is greatest in the CBT-DC group) will allow group differences obtained to be attributed to the action of the targeted mechanisms.

2.5 Time-Dependent Effects: Explore time-dependent effects between mechanism process measures and alcohol outcomes from BL through 1-mo, 4-mo, and 8-mo FU assessments. These results will allow for causal inferences between mechanisms and outcomes by demonstrating temporal priority in change.

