7.8. Mechanism manipulation checks

The specific aims of this clinical research are to demonstrate the group differences in clinical outcomes predicted above. However, inferring that these differences were due the mechanisms targeted in the specific groups require demonstrating that the levels of change in the mechanisms as a result of treatment varied according to the group assignments as expected. This will be done using the anxiety reduction and de-coupling process measures described above taken at the pre-treatment baseline compared to the immediate post-treatment assessment. Given our sample size of 100 subjects per group, we will have 80% power to detect group differences of 0.40 SD units using a two-tailed test and a 0.05 alpha level. Since this minimally detectable ES is less than half of the natural variability of the measure and, therefore, on the low end of clinical and theoretical significance (e.g., Ferguson, 2009), our difficulty in detecting even smaller effects is not considered problematic.

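### The mechanism manipulation check is described as a comparison of change with no routine baseline adjustment, and its 0.40 SD detectable difference carries no pre-post correlation and no clear SD scale

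*Combined protocol and SAP*

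**What the plan says.** Section 2.4 of the combined protocol and SAP sets out the check in one instruction: "Compare groups on pre- to post-treatment change in mechanism process measures". Section 7.8 says the process measures are those "taken at the pre-treatment baseline compared to the immediate post-treatment assessment", and that the aim is to show that "the levels of change in the mechanisms as a result of treatment varied according to the group assignments as expected". Neither section names a test, a regression model or a baseline covariate.

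The sizing statement in 7.8 opens with "Given our sample size of 100 subjects per group" and continues: "we will have 80% power to detect group differences of 0.40 SD units using a two-tailed test and a 0.05 alpha level". It is then defended as small enough: "Since this minimally detectable ES is less than half of the natural variability of the measure". No pre-post correlation is given, there or elsewhere.

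Three other places matter:

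- Section 7.4 brings baseline variables into the analyses only if the groups differ significantly on them.
- Section 7.5 names mixed models and GEE, but for the alcohol hypotheses.
- Section 6.8.5 makes latent fear and distress factors the primary anxiety process measures. The de-coupling measures in 6.8.6 are observed questionnaire scores.

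**The concern.** The power of a comparison of change depends on how strongly the baseline and post-treatment scores are correlated. The power statement contains no correlation, so it cannot be matched to the comparison described without a further assumption. The scale is also unclear. A test on change scores naturally yields a detectable difference in SDs of change, while the justification in 7.8 treats the 0.40 as a fraction of the SD of the measure.

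There is also a more efficient analysis at hand. Table 2 schedules the questionnaires at both baseline and post-treatment. In a randomized comparison, adjusting the post-treatment score for its baseline value is never less precise, in large samples, than comparing change.

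The check carries weight because Sections 2.4 and 7.8 make attribution of any alcohol difference to the targeted mechanisms depend on it. It is nevertheless a supporting analysis, which 7.8 itself separates from the specific aims.

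**Working it through.** **Inputs.** From Section 7.8: n = 100 per group, 80% power, two-sided alpha 0.05, difference 0.40 SD. Assumed, because the documents do not give them: the pre-post correlation r, shown over a range, and equal SDs at the two visits.

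**Step 1: reproduce the stated figure.** For two groups with unit SD, the normal approximation gives (1.960 + 0.842) × sqrt(2/100) = 0.396 SD. The noncentral t gives 0.398 SD, and 80.4% power for 0.40 SD. The stated figure is therefore correct as a plain two-sample comparison. No correlation term enters.

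**Step 2: change scores, SD of the measure.** With equal SDs, the SD of change is SD × sqrt(2(1 − r)), so the detectable difference is 0.398 × sqrt(2(1 − r)). At r = 0.3 this is 0.398 × 1.183 = 0.47. It is no larger than 0.40 when 2(1 − r) ≤ (0.40/0.398)² = 1.010, that is, when r is at least about 0.495.

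**Step 3: baseline-adjusted post score.** The residual SD is SD × sqrt(1 − r²), so the detectable difference is 0.398 × sqrt(1 − r²). At r = 0.3 this is 0.398 × 0.954 = 0.38.

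**Step 4: results at 100 per group.** Differences are in SDs of the measure. Power is for a true difference of 0.40 SD, from the noncentral t with the effect divided by the factor in Step 2 or 3.

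| r | Detectable, change | Detectable, adjusted | Power, change | Power, adjusted |
|---|---|---|---|---|
| 0.3 | 0.47 | 0.38 | 66% | 84% |
| 0.5 | 0.40 | 0.34 | 80% | 90% |
| 0.7 | 0.31 | 0.28 | 95% | 98% |
| 0.8 | 0.25 | 0.24 | 99.4% | 99.7% |

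**Step 5: relative efficiency.** The variance ratio, adjusted to change, is (1 − r²)/(2(1 − r)) = (1 + r)/2. That is 0.65 at r = 0.3, 0.75 at r = 0.5 and 0.85 at r = 0.7. At r = 0.5 the adjusted analysis needs 74 per group for 0.40 SD, against 99 for change scores (normal approximation).

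The ordering does not need equal SDs. With baseline SD s0 and post-treatment SD s1, the variance of change is s0² + s1² − 2·r·s0·s1 = (s0 − r·s1)² + s1²(1 − r²), which is at least the adjusted variance s1²(1 − r²).

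**Step 6: the other reading of the scale.** If the 0.40 is in SDs of change, the figure holds at every r. In SDs of the measure it then equals 0.40 × sqrt(2(1 − r)): 0.47 at r = 0.3 and 0.31 at r = 0.7. The comparison with the spread of the measure no longer follows from the number 0.40.

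**The case against.** The strongest reply is that no raw change-score test has been specified. Change may describe the target of inference, which a baseline-adjusted model, a mixed model or a latent-variable model could all serve. This stands. A reader might infer that the plan has chosen change scores over adjustment, but the documents name no model. The supportable criticism is that the only comparison described is one of change, and that the adjustment rule in 7.4 would leave a balanced baseline score out.

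A reader might also infer that the 0.40 SD holds only at r = 0.5. It does not: it is met or bettered at any r of about 0.5 or more, and it holds at every r on the SD-of-change scale.

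Section 6.8.5 is a further fair point. For latent fear and distress, the observed-score formulas above do not carry over directly, so any fix must cover those measures separately.

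The figure of 100 per group may be conservative. It rests on four-month follow-up (Section 6.1), while the post-treatment visit takes place before discharge. If all 350 attended (about 116 per group), the plain detectable difference would be about 0.37 SD, and change-score power for 0.40 SD at r = 0.3 about 73%. Attendance at that visit is not given.

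Finally, it is tempting to use the d = .29 between CBT and relaxation training in Section 4.3 to call the check underpowered. That value is a four-month result on the proportion above a trait-anxiety threshold, in a different contrast, so it is no benchmark for post-treatment differences among these arms. Nor do the documents say that a null check would be read as proof that the mechanism was not moved. Section 7.8 states a condition for attribution and accepts that smaller effects may be missed.

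**Conclusion.** The stated 0.40 SD is arithmetically right for a plain two-sample comparison. What is missing is the link to the analysis described: the model, the SD scale and the correlation.

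On the reading that fits the wording of 7.8 best (change scores, SD of the measure, equal SDs), the claim of 80% power for 0.40 SD is safe at r of about 0.5 or more and fails below it, with about 66% power at r = 0.3. On the other reading the figure stands but its justification does not. Whether there is any real shortfall is unknown, because the documents give no r.

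Baseline adjustment removes the dependence: for observed continuous scores, the detectable difference stays at or below 0.40 SD whatever r is. The gain is material at low r (66% to 84% at r = 0.3) and small at high r (95% to 98% at r = 0.7). The point is worth acting on because it costs nothing, but it concerns a supporting analysis and does not touch the primary, secondary or tertiary aims.

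**What to change.** In Sections 2.4 and 7.8, state that groups are compared on the post-treatment process score, with the baseline value of the same score and the trait-anxiety randomization stratum (Section 7.3) as covariates, whether or not the groups differ at baseline. For latent fear and distress, regress the post-treatment factor on the baseline factor and arm.

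Restate the detectable difference, for observed continuous scores, as about 0.40 × sqrt(1 − r²) SDs of the measure. Take r from the parent study, or show a range: 0.38 at r = 0.3, 0.34 at r = 0.5, 0.28 at r = 0.7. Say explicitly that the SD is that of the measure, so that the justification in 7.8 refers to the same scale.

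The cost is wording in two sections and one degree of freedom per covariate. No new data, visits or patients are needed.

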We propose to recruit 350 patients to obtain a final sample of 300 cases with baseline and follow-up data who are randomized to one of three study groups: 1) six sessions of CBT for anxiety reduction (CBT-AR); 2) six sessions of CBT for anxiety-alcohol de-coupling (CBT-DC); or, 3) the original CBT from the parent R01 with three sessions devoted to anxiety reduction and to anxiety-alcohol de-coupling each (CBT-O). To enhance feasibility of the renewal work and ensure its continuity/interpretability with the parent R01, the population and procedures of the proposed work are matched to those used in the parent R01. In brief, alcohol dependent individuals with a co-occurring anxiety disorder will be enrolled within one week of beginning the 28-day residential alcohol use disorder (AUD) treatment program, "Lodging Plus." Patients will undergo five significant assessments: 1) Baseline Assessment (after being deemed eligible but prior to randomization); 2) Post-Treatment Assessment (immediately following the conclusion of the six-session treatment and prior to being discharged from Lodging Plus); 3) One-Month Follow-Up Assessment (30 days following completion of the study treatment); 4) Four-Month Follow-Up Assessment (120 days following completion of the study treatment); and, 5) Eight-Month Follow-Up Assessment (240 days following completion of the study treatment). Primary alcohol outcomes measures will include categorical variables (any alcohol use) and percent or count variables (e.g., days drinking, drinks per drinking occasion). We will also measure alcohol dependence and hazardous drinking statuses at follow-ups. Predictions are based on the parent R01 findings suggesting (but not demonstrating) a dose-dependent positive relationship for de-coupling therapy elements but not anxiety reduction therapy elements in terms of alcohol outcomes; i.e., CBT-DC > CBT-O > CBT-AR on alcohol outcomes. As a means of confirming that the therapeutic mechanisms targeted were responsible for the group differences obtained, process measures of the therapeutic mechanisms are included at all assessments both to verify their dose-dependent activation in groups and to track temporal patterns of change on the mechanisms relative to the outcomes over follow-ups.

Study Aims:

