5.0 RESEARCH DESIGN

5.1 . Overview.

This is a between-group randomized clinical trial with 350 patients to randomized to one of three study groups: 1) six sessions of CBT for anxiety reduction (CBT-AR); 2) six sessions of CBT for anxiety-alcohol de-coupling (CBT-DC); or, 3) the original CBT from the parent R01 with three sessions devoted to anxiety reduction and three sessions devoted to anxiety-alcohol de-coupling (CBT-O). Alcohol dependent individuals with co-occurring SAD, GAD or PD/Ag will be enrolled within one week of beginning the 28-day residential AUD treatment program, Fairview "Lodging Plus" in Minneapolis. All study treatments will take place while patients are still in the Lodging Plus program; i.e., one hour sessions during patient free-time (i.e., no conflicting programming) for six consecutive business days. Patients will undergo four significant assessments: 1) baseline (after being deemed eligible but prior to randomization); 2) post-treatment (immediately following conclusion of the six-session treatment and prior to being discharged from Lodging Plus; 3) one-month (30 days following completion of the

study treatment); and, 4) four-months (120 days following completion of the study treatment); 5)) Eight-Month Follow-Up Assessment (240 days following completion of the study treatment). Primary relapse measures will include categorical (any alcohol use, hazardous drinking, alcohol dependence) and continuous/counts (e.g., days drinking, drinks per drinking occasion, binge days) variables. Following approval of MOD00013885 we will not complete the eight-month follow-up assessment on recruited participants. Because the primary outcomes for this study will be collected at the four-month follow-up appointment, this modification will allow us to continue recruitment through February 2020, with recruited participants able to complete the four-month follow-up prior to the end of the funding period for this project in June 2020.

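### Sections 2.4 and 2.5 claim causal attribution to mechanisms that neither temporal priority nor a manipulation check can support, because only therapy arm is randomised

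*Combined protocol and SAP*

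**What the plan says.** Two sentences in section 2.0 state what the mechanism results will license. Section 2.4 compares the arms on change in the process measures from before to after treatment, and says that a dose-dependent pattern "will allow group differences obtained to be attributed to the action of the targeted mechanisms". Section 2.5 sets out to "Explore time-dependent effects between mechanism process measures and alcohol outcomes from BL through 1-mo, 4-mo, and 8-mo FU assessments", and concludes: "These results will allow for causal inferences between mechanisms and outcomes by demonstrating temporal priority in change".

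The Design Overview says the same in stronger terms: "As a means of confirming that the therapeutic mechanisms targeted were responsible for the group differences obtained, process measures of the therapeutic mechanisms are included". The Schema section repeats this.

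What is randomised is the arm. Section 5.1 reads: "This is a between-group randomized clinical trial with 350 patients to randomized to one of three study groups".

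The statistics section covers less ground. Section 7.8 specifies a comparison of arms on process measures "taken at the pre-treatment baseline compared to the immediate post-treatment assessment". Its wording is more careful: "inferring that these differences were due the mechanisms targeted in the specific groups require demonstrating that the levels of change in the mechanisms" varied by arm as expected. That makes the check a requirement for the inference and does not call it sufficient. The readable text gives no model for the 2.5 analysis. The one covariate rule, in section 7.4, brings in baseline variables on which the arms differ significantly. The reference list includes a paper on the moderator-mediator distinction, but no readable section applies it.

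**The concern.** The two sections fail for different reasons.

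**Section 2.5.** A patient's expectancies or anxiety after treatment, and that patient's later drinking, may both reflect something else, such as motivation or severity. Time order rules out later drinking as the cause of the earlier score. It does not rule out a common cause, and randomising the arm does not remove one that operates within arms. Section 7.4 does not help, because it deals with imbalance between arms, whereas the confounding here is between mechanism and outcome.

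**Section 2.4.** The arm comparison is randomised, so a difference in mechanism change is a valid estimate of the therapy's effect on that score. The faulty step is the next one. If the arm changed the mechanism and the arm changed drinking, it does not follow that the first change produced the second. The therapy may work by another route.

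At stake is the interpretation of why the arms differ. A mechanism could be reported as the cause of better outcomes when it had no effect on them.

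**Working it through.** **1. The plan's own figure.** Section 7.8 states: "Given our sample size of 100 subjects per group, we will have 80% power to detect group differences of 0.40 SD units", two-tailed at 0.05.

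- Power = Φ(0.40/√(2/100) − 1.96) = Φ(2.828 − 1.96) = Φ(0.868) = 0.807.
- A t-based calculation gives 0.804, and 99 per group are needed.

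The figure reproduces. It is the power to see the arms differ on a mechanism, and says nothing about whether the mechanism affects drinking.

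**2. A null lagged association with a shared cause (section 2.5).** Inputs: n = 300 (the target with follow-up data), and n = 262 (75% of 350 = 262.5, using the retention estimate in section 4.3). The documents give no confounding strength. Assume one unmeasured factor that correlates *a* with the earlier mechanism score and, in absolute value, *a* with later drinking, with no causal effect between the two.

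- Induced correlation: r = a × a.
- Chance of significance (Fisher z, two-sided 0.05): Φ(δ − 1.96) + Φ(−δ − 1.96), where δ = √(n − 3) × atanh(r).

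| a | r | δ, n = 300 | significant, n = 300 | δ, n = 262 | significant, n = 262 |
|---|---|---|---|---|---|
| 0.2 | 0.04 | 0.69 | 11% | 0.64 | 10% |
| 0.3 | 0.09 | 1.56 | 34% | 1.45 | 31% |
| 0.4 | 0.16 | 2.78 | 79% | 2.60 | 74% |

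Without confounding the figure would be 5%.

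**3. The same question with the plan's own effect sizes.** A simulation of 4,000 trials per setting used two arms of 100 (CBT-AR and CBT-DC), the 0.40 SD arm effect on the mechanism, and relapse of 53% and 21% (section 7.5) produced directly by arm. The true effect of mechanism on relapse was zero. A shared baseline factor explained an assumed share of the variance in both the mechanism score and the relapse propensity. The lagged test was adjusted for arm.

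| Shared variance | Manipulation check significant | Lagged test significant | Lagged test, shared factor adjusted for | Check, arm difference and lagged test all significant |
|---|---|---|---|---|
| 0 | 80% | 5% | 5% | 4% |
| 0.10 | 79% | 20% | 6% | 16% |
| 0.20 | 81% | 59% | 6% | 48% |
| 0.30 | 81% | 91% | 5% | 73% |

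Two things follow. The manipulation check passes at the same rate whatever the confounding, so it cannot detect the problem. Adjusting for the shared factor, where it is measured, restores roughly the nominal rate.

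**4. Section 2.4 without any shared cause.** In the first row the check is significant in 80.2% of trials and the arm difference in relapse in 99.9%. Both therefore occur together in at least 80.2 + 99.9 − 100 = 80.1% of trials, although the mechanism has no effect on relapse. This is a deliberately extreme case, in which the whole arm effect goes by another route, and it uses two arms rather than the three-arm dose ordering. It shows that the criterion can be met with no mechanism effect; it does not estimate how often that would happen here.

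**The case against.** The strongest reply is that the plan is more modest than these sentences suggest. Section 2.5 is labelled exploratory. Section 7.8 treats the check as necessary and already uses the immediate post-treatment score. For alcohol outcomes, section 7.5 names mixed models and GEE that can carry time-dependent covariates. All arms receive six sessions with common elements, and fidelity review covers contamination, which narrows the alternative routes. Baseline drinking, the Addiction Severity Index and the Obsessive-Compulsive Drinking Scale are collected, so part of any confounding by severity is measurable. The confounding strengths above are assumed, and the mildest gives only about twice the nominal error rate.

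Most of this stands, and it limits the size of the point. It does not remove it: nothing in the readable text withdraws the two claims or commits the mechanism analysis to adjusting for those covariates.

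A reader might go further in four ways that the documents do not support.

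- *That a false mechanism will be reported.* This requires a sufficiently strong shared cause or alternative route, and the documents show neither. The plan also gives no decision rule for 2.5 from which an error rate could be fixed.
- *That a shared baseline cause also undermines 2.4.* Randomisation balances such a cause between arms in expectation. The weakness of 2.4 is the alternative route.
- *That mechanism attribution is the trial's headline purpose.* The Study Aims list three arm comparisons on alcohol outcomes, and section 7.8 describes the specific aims as group differences in clinical outcomes.
- *That follow-up process scores are paired with drinking that preceded them.* No section states the pairing. The Timeline Follow-Back gives daily drinking between assessments (section 6.8.3), so an earlier score can be set against later drinking.

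**Conclusion.** The causal sentence in 2.5 and the attribution sentence in 2.4 claim more than the design supports. Temporal order alone does not exclude a common cause, and a passed manipulation check does not show that the mechanism carried the effect.

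A null lagged association could be significant in about 11% to 79% of trials at n = 300 for an unadjusted correlation, over assumed shared-factor correlations of 0.2 to 0.4. These figures illustrate sensitivity to an unknown and do not predict what this trial would find. The randomised comparisons in Aims 1 to 3, and the arm comparison of mechanism change itself, are unaffected. This is a low-severity point about interpretation, but the text is wrong as written and cheap to correct.

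**What to change.** **Wording.** In sections 2.4 and 2.5, and in the matching sentences of the Design Overview and the Schema section, replace the claims of causal inference, attribution and confirmation with a statement that the results would be *consistent with* the proposed mechanism.

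**Analysis.** Prespecify one exploratory model:

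- mediator: the post-treatment process score, taken before discharge;
- outcome: Timeline Follow-Back drinking on days after that visit;
- estimand: the indirect effect of randomised arm through the mediator, with a confidence interval (a bootstrap interval is one acceptable choice);
- adjustment: baseline mechanism score, baseline drinking and baseline severity where collected;
- assumption: no unmeasured mediator-outcome confounding, stated openly;
- sensitivity analysis: how strong such confounding would have to be to remove the indirect effect.

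Using the post-treatment score also reduces reliance on the eight-month visit, which section 5.1 drops following a modification.

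**Cost.** SAP text and a little more analysis on data already collected. The real price is a weaker mechanism claim.
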